10 SAFETY EVALUATION

Adverse Events

10.1.1 Definition

An adverse event or adverse experience (AE) is any untoward medical occurrence associated with the use of a drug in humans, whether or not considered drug related. Therefore, an AE can be ANY unfavorable and unintended sign (including an abnormal laboratory finding), symptom, or disease temporally associated with the use of a medicinal (investigational) product, whether or not considered related to the medicinal (investigational) product (attribution of 'unrelated', 'unlikely', 'possible', 'probable', or 'definite').

An AE is considered "unexpected" if it is not listed in the investigator brochure or is not listed at the specificity or severity that has been observed; or if an investigator brochure is not required or available, is not consistent with the risk information described in the general investigational plan in other study-related documents.

10.1.1.1 Diagnosis Versus Signs and Symptoms

If known, a diagnosis should be recorded on the CRF rather than individual signs and symptoms (e.g., record only liver failure or hepatitis rather than jaundice, asterixis, and elevated transaminases). However, if a constellation of signs and/or symptoms cannot be clinically characterized as a single diagnosis or syndrome at the time of reporting, each individual event should be recorded as an AE or SAE on the CRF. If a diagnosis is subsequently established, it should be reported as follow-up information.

10.1.1.2 Adverse Events Occurring Secondary to Other Events

In general, AEs occurring secondary to other events (e.g., cascade events or clinical sequelae) should be identified by their primary cause. For example, if severe diarrhea is known to have resulted in dehydration, it is sufficient to record only diarrhea as an AE or SAE on the CRF.

However, clinically significant AEs occurring secondary to an initiating event that are separated in time should be recorded as independent events on the CRF. For example, if a severe gastrointestinal hemorrhage leads to renal failure, both events should be recorded separately on the CRF.

10.1.1.3 Abnormal Laboratory Values

Only clinically significant laboratory abnormalities that require active management will be recorded as AEs or SAEs on the CRF (e.g., abnormalities that require study drug dose modification, discontinuation of study treatment, more frequent follow-up assessments, further diagnostic investigation, etc.).

If the clinically significant laboratory abnormality is a sign of a disease or syndrome (e.g., alkaline phosphatase and bilirubin 5 x the upper limit of normal associated with cholecystitis), only the diagnosis (e.g., cholecystitis) needs to be recorded on the Adverse Event CRF.

If the clinically significant laboratory abnormality is not a sign of a disease or syndrome, the abnormality itself should be recorded as an AE or SAE on the CRF. If the laboratory abnormality can be characterized by a precise clinical term, the clinical term should be recorded as the AE or SAE. For example, an elevated blood potassium level of 7 mEq/L should be recorded as "hyperkalemia".

Observations of the same clinically significant laboratory abnormality from visit to visit should not be repeatedly recorded as AEs or SAEs on the CRF, unless their severity, seriousness, or etiology changes.

10.1.1.4 Preexisting Medical Conditions (Baseline Conditions)

A preexisting medical condition should be recorded as an AE or SAE only if the frequency, severity, or character of the condition worsens during the study. When recording such events on an Adverse Event CRF, it is important to convey the concept that the preexisting condition has changed by including applicable descriptors (e.g., "more frequent headaches").

10.1.2 Grading and Relationship to Drug

The descriptions and grading scales found in the CTEP Version 5 of the NCI Common Terminology Criteria for Adverse Events (CTCAE) will be utilized for AE reporting. CTEP Version 5 of the CTCAE is identified and located at: http://ctep.cancer.gov/protocolDevelopment/electronic applications/ctc.htm.

AEs not covered by specific terminology listed should be reported with common medical terminology and documented according to the grading scales provided in the CTCAE Version 5.0.

The relationship of event to study drug will be documented by the Investigator as follows:

- Unrelated: The event is clearly related to other factors such as the participant's clinical state, other therapeutic interventions or concomitant drugs administered to the participant.
- Unlikely: The event is doubtfully related to investigational agent(s). The event was most likely related to other factors such as the participant's clinical state, other therapeutic interventions, or concomitant drugs.
- Possible: The event follows a reasonable temporal sequence from the time of drug administration but could have been produced by other factors such as the participant's clinical state, other therapeutic interventions or concomitant drugs.
- Probable: The event follows a reasonable temporal sequence from the time of drug administration and follows a known response pattern to the study drug. The event cannot be reasonably explained by other factors such as the participant's clinical state, therapeutic interventions or concomitant drugs.
- Definite: The event follows a reasonable temporal sequence from the time of drug administration, follows a known response pattern to the study drug, cannot be reasonably explained by other factors such as the participant's condition, therapeutic interventions or concomitant drugs; AND occurs immediately following study drug administration, improves upon stopping the drug, or reappears on re-exposure.

(Regardless of Expectedness)									
Attribution	Grade 1	Grade 2	Grade 3	Grade 4					
Unrelated			Х	Х					
Unlikely			X	Х					
Possible	X	Х	Х	Х					
Probable	X	Х	Х	Х					
Definite	X	X	X	X					

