6.1.10 Risks and Benefits

This is a Greater Than Minimal Risk study according to IRB criteria. Phototoxicity is the most likely potential risk associated with the systemic administration of the porfimer sodium. Proper shielding from the operating room lights will be maintained and the pulse oximetry sensor will be rotated every 20 - 30 minutes to minimize this risk. The subjects will be provided with written instructions on how to protect themselves from excessive light exposure.

The site-specific toxicity associated with this therapy includes:

- Injection site reaction: Very common effects include pain at the injection site (12%) which is transient and can be minimized by slowing the injection rate. Common effects include injection site reaction (3%) and burning sensation (3%).
- Tumor/local tissue reaction: Very common effects include pain (15%), hemorrhage (15%) and scarring (12%). Common effects include edema (8%), localized infection (8%), fever (8%), and skin necrosis (2%).
- Phototoxicity: Common effects include sunburn (3%), blisters (5%), erythema (5%), hyper-pigmentation (3%), and cutaneous photosensitivity (3%).
- Other systemic events: Constipation (11%), vomiting (9%), anemia (8%), nausea (6%), and giddiness (2%).

Potential Procedural Risks of EBUS-TBN Guided I-PDT and/or I-PDT and/or PDT

- Bronchial bleeding from the insertion site
- Extension of the bronchoscopic procedure duration
- Minimal risk of pneumothorax, infection, mediastinitis, allergic reaction to porfimer sodium
- Airway perforation

Standard of care palliative radiotherapy followed by I-PDT. It is not known what the risk is for administering the I-PDT two days after standard of care palliative radiotherapy.

Potential Benefits of the Proposed Research

For participants that have partial or complete response to I-PDT and/or PDT, the potential benefits include a significant reduction in tumor mass and symptoms. There is no guarantee of the outcome, nor is it possible to predict whether or not any specific participant will respond to porfimer sodium I-PDT and/or PDT.

The data that will be collected in this study will allow the research team to evaluate the safety and provide indication on the potential efficacy of this treatment. If shown to be safe, we will use this data to design Phase I/II studies to confirm safety and test the efficacy of EBUS-TBN guided I-PDT with porfimer sodium.

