12.1.9 Safety Monitoring Lead-In (Cohort B)

The safety profile will be measured by recording treatment related AEs that are \geq grade 4 with attribution of 'possible', 'probable', or 'definite', according to the NCI CTCAE v5.0. The safety measures will be evaluated in all patients who received image-guided I-PDT preceded by standard of care p-XRT of 8 Gy x1 for the treating their MCAO. The following decision rules will be followed: (i) If 0/3 AE \geq grade 4's are observed it will be concluded the therapy is safe. (ii) If 1/3 AE \geq grade 4's are observed, enroll 3 more patients for safety evaluation. If 1/6 AE \geq grade 4's are observed it will be concluded the therapy is safe. If \geq 2/6 AE \geq grade 4's are observed it will be concluded that therapy is unsafe. We calculated via Monte Carlo simulation that if the AE \geq grade 4 rate is 20%, 30% and 40% the respective probabilities of declaring the treatment unsafe are 0.26, 0.51 and 0.70.

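### The Cohort B safety lead-in counts treatment-related grade 4+ events, but its attribution levels are defined only for the study drug, so an event blamed on needle placement or radiotherapy could be left out of the count

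*Combined protocol and SAP*

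**What the plan says.** Section 12.1.9 sets the counted event for the lead-in: "The safety profile will be measured by recording treatment related AEs that are" grade 4 or higher, "with attribution of 'possible', 'probable', or 'definite', according to the NCI CTCAE v5.0". The population is "patients who received image-guided I-PDT preceded by standard of care p-XRT of 8 Gy x1". No event in three patients means safe. With one in three the rule is "observed, enroll 3 more patients for safety evaluation". One in six then means safe, and two or more in six means unsafe.

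The attribution levels are defined in section 10.1.2, whose title names the drug: "The relationship of event to study drug will be documented by the Investigator as follows". *Unrelated* reads "The event is clearly related to other factors such as the participant's clinical state, other therapeutic interventions or concomitant drugs administered to the participant". *Unlikely* uses the same list for events most likely due to such factors. *Possible* covers an event that follows drug administration in a reasonable time sequence but that one of those factors could also have produced. *Probable* and *definite* require that no such factor reasonably explains the event.

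Section 6.1.10 lists procedural risks, among them bleeding at the insertion site, airway perforation, pneumothorax and mediastinitis. On the Cohort B sequence it says: "It is not known what the risk is for administering the I-PDT two days after standard of care palliative radiotherapy".

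**The concern.** The lead-in exists to test a sequence whose risk the protocol calls unknown, and it is the only numerical safety rule for Cohort B. Section 12.1.8 is descriptive and the interim look in 12.1.7 concerns futility. Two parts of the sequence, the transbronchial needle and the radiotherapy, are not the study drug. The protocol repeatedly calls the radiotherapy standard of care, which invites an investigator to treat it as an *other* intervention.

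If 10.1.2 is applied as written, a grade 4+ event that the investigator confidently assigns to one of those parts falls into a level that 12.1.9 does not count. The gate could then pass on a count that omits harm from the regimen under test. With three to six patients, a single classification can decide the result.

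**Working it through.** **Which object each section names**

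- 10.1.1 and 10.1.2: the investigational product, or study drug. Only 10.1.2 defines the five levels.
- 10.1.5 (late serious events): the study intervention. No scale is defined for it.
- 10.1.6 (Unanticipated Problems): the research procedures. It explains what possibly related means, but for that reporting route only.
- 12.1.2 (Cohort 0): I-PDT and/or PDT treatment, with the same three counting levels and no definition of its own.
- 12.1.9 (Cohort B lead-in): treatment, in patients given radiotherapy and then I-PDT. It has no definition of its own. It cites CTCAE v5.0, but 10.1.2 uses CTCAE for event descriptions and grading and sets out attribution separately.

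None of the wider wordings amends 10.1.2 for the lead-in count.

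**Effect of one call**

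- One true event in the first three, rated unlikely: 1/3 becomes 0/3. The therapy is declared safe and the three extra patients are not required.
- One true event in the first three and one in the next three, with the second rated unlikely: 2/6 becomes 1/6, and unsafe becomes safe.

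**Operating characteristics**

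Let p be the true per-patient probability of a regimen-caused grade 4+ event. Section 12.1.9 does not write out two or three events in the first three patients; I take these as unsafe. Then

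P(unsafe) = 1 − [(1−p)³ + 3p(1−p)²(1−p)³] = 1 − (1−p)³ − 3p(1−p)⁵.

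The plan's own figures come first:

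- p = 0.20: 1 − 0.512 − 0.197 = 0.291 (plan 0.26)
- p = 0.30: 1 − 0.343 − 0.151 = 0.506 (plan 0.51)
- p = 0.40: 1 − 0.216 − 0.093 = 0.691 (plan 0.70)

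The 30% and 40% entries reproduce to within a point. The 20% entry is 3.1 points off and is a separate matter that is not used here.

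Now let c be the share of those events rated possible or higher under 10.1.2, and replace p by c·p. The documents give no value for c, so it is an assumption shown as a range. Treating it as a simple multiplier supposes that each event is classified independently.

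| True rate | c = 1 | c = 0.75 | c = 0.50 |
|---|---|---|---|
| 20% | 0.291 | 0.186 | 0.094 |
| 30% | 0.506 | 0.346 | 0.186 |
| 40% | 0.691 | 0.506 | 0.291 |

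For example, p = 0.40 with c = 0.50 gives c·p = 0.20 and P(unsafe) = 0.291. The plan's 0.51 and 0.70 are therefore reached only if every regimen-caused event is counted.

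**The case against.** The strongest reply is that *possible* catches most of what matters. Porfimer is given 48 ± 4 hours before light (6.1.1), so an event on or soon after the procedure day can meet the time condition. A cause that merely could lie elsewhere does not take the event out of the count. This stands: exclusion needs a judgment that the cause is clearly or most likely something other than the drug.

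A reader might infer that any life-threatening bleed at the fiber site would be excluded. The documents do not support that. Section 6.1.10 also lists hemorrhage (15%) among the local tissue reactions to the therapy, so *possible* is a natural rating; such a bleed could be excluded, but need not be. Nor is light injury a good example, because the light acts through the photosensitizer and the damage may fit a drug response pattern. The last conditions of *definite* are alternatives joined by *or*, so they do not make that level unreachable, and *possible* is enough to count in any case.

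It can also be said that 12.1.9 speaks of treatment and describes the whole sequence, so that *other* interventions means those outside the study. That is a reasonable reading, but no section states it. The *probable* and *definite* definitions list therapeutic interventions among the competing explanations without the word *other* directly before them, which weakens it.

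Finally, events left out of the count are not lost. The routine reporting table in 10.1.3 takes grade 3 and 4 events whatever the attribution, grade 3 and above enter the safety analysis, serious events go to the sponsor within 24 hours (10.1.5), and the monitoring committee can recommend suspension or termination (section 11). These limit the consequence, but they do not correct the lead-in count.

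**Conclusion.** The point holds as a mismatch of definitions. Taken literally, 10.1.2 lets a grade 4+ event judged clearly or most likely due to needle placement or to the 8 Gy fraction stay out of the 12.1.9 count, and one such call can change the result from unsafe, or from expansion, to safe. Needle injury and radiotherapy harm are the clear cases.

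The probabilities show how sensitive the rule is to lost events; they do not estimate the loss. A reader might infer that the scale in fact halves the chance of stopping. Nothing in the documents supports a particular capture share, and because mixed-cause events count, the loss could be close to nil. The figures also assume that two or more events in the first three mean unsafe, and that classification is independent across patients.

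**What to change.** Reconcile 10.1.2 with 12.1.9 so that both refer to the whole study regimen:

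- In 10.1.2, record attribution separately for porfimer, for the fiber placement/light procedure and, in Cohort B, for the palliative radiotherapy.
- In 10.1.2, state that other therapeutic interventions means treatments outside the study regimen.
- In 12.1.9, state that a grade 4+ event rated possible or higher for any one component enters the count.

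The cost is protocol wording, plus attribution fields if the adverse event form lacks them. The form is not in the documents; Appendix C asks for attributions on the serious event forms without saying to what. The small downside is that slightly more events may enter the lead-in count.

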10.1.3 Reporting Adverse Events

Table 2Guidelines for Routine Adverse Event Reporting for Phase 2 Studies
(Regardless of Expectedness)

Routine AEs occurring between the start date of intervention until 30 days after the last intervention, or until the event has resolved, the study participant is lost to follow-up, the start of a new treatment, or until the study investigator assesses the event(s) as stable or irreversible, will be reported. New information will be reported after it is received.

Adverse events will be graded from 1 to 5. Mild and moderate side effects are common after therapeutic bronchoscopy for central airway tumors. Therefore, grade 3 or above will be included in safety analysis, and grades 1 and 2 will be collected and reported.

Serious Adverse Events

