PDT's primary indication is for obstructive disease and symptom palliation in patients with tumors that are not eligible for standard surgery and radiation therapy. Currently, the most commonly used photosensitizer in PDT is Photofrin[®] (Pinnacle Biologics Inc. Bannockburn, IL). After intravenous injection, Photofrin[®] is retained in neoplastic cells and, to a lesser degree, in normal tissue. The therapeutic effect is obtained by illuminating the target tumor and margins with visible light with 630 ± 3 nm wavelength, approximately 48 hours post-administration. (19-21) Photosensitivity is the major complication of PDT with Photofrin[®]. The photosensitivity usually lasts for 4-6 weeks. During that time, patients are instructed to use sunglasses to protect the eyes and cover the skin with long sleeve shirts and pants, when exposed to direct sunlight or bright indoor light. The development of second-generation PSs has minimized photosensitivity, by having fast accumulation and clearance.

1.1.3 **Photofrin® (Porfimer Sodium)**

Photofrin® for injection is supplied as a freeze-dried cake or powder as follows: NDC 76128-155-75, 75 mg vial.

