6.1.7 Precautions When Using Porfimer Sodium

Light-avoidance measures for approximately 30-90 days will be required. The clinical research coordinator and staff nurses will explain the light-avoidance measures to each subject, and a written instructions leaflet will be handed out to the subjects (**Appendix B**). The subject will be cautioned to protect the site of the infusion from excessive direct sunlight and certain bright lights for up to 3 months. The site may be exposed to normal ambient light.

Vital signs will be taken immediately after the end of the injection and 15 minutes after.

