6.1.8 Duration of Treatment

The porfimer sodium photosensitizing drug will be given as a single dose 48 ± 4 hours (Day -2) before the EBUS I-PDT. The treatment is expected to be completed within a few hours.

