8.1.8 Initial Follow-Up Evaluation

The following evaluations will be performed **4 weeks** (± **1 week**) after the last study I-PDT and/or PDT (*unless otherwise indicated**):

- Physical examination (including vital signs)
- Hematology: Complete blood count (CBC) with automated differentials.
- Chemistry: Complete metabolic panel (CMP).
- Blood draw for immune markers
- ECOG Performance Status (Appendix A)
- Tumor/Disease Assessment: Chest CT scan
- Concomitant medications
- Quality of Life Questionnaire (Cohorts A and B; Appendix D)
- Adverse events (will be followed for 30 days following treatment/procedure)
- Schedule date/time for follow-up bronchoscopy with EBUS (without TBNA). TBNA will be performed only if clinically indicated outside the scope of this study. If a tumor is visible, tumor tissue biopsies (about 50-300 mg per biopsy, if feasible) will be collected for immune markers. NOTE: The bronchoscopy will not be performed at this visit.
- If EBUS is performed and a tumor is visible, tumor tissue biopsies (about 50-300 mg per biopsy, if feasible) will be collected for immune markers.

*Bronchoscopic and ultrasound images that are routinely obtained during therapeutic procedures will be used to evaluate the airway initially and during follow up. *Note: Initial follow-up bronchoscopy will be performed within 4 weeks following the first follow-up visit. Additional bronchoscopies will be performed as clinically indicated.*

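### New non-serious phototoxicity starting more than 30 days after treatment is not systematically collected, although the plan's own light precautions run to about 90 days

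*Combined protocol and SAP*

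**What the plan says.** **Collection window.** Section 10.1.3 covers "Routine AEs occurring between the start date of intervention until 30 days after the last intervention". It then lists alternative end points, among them resolution of the event, which reads as continued follow-up of events that have already begun. Section 8.1.8 repeats the 30-day limit at the initial follow-up (4 ± 1 weeks). In Table 1 (section 8.1.11) the adverse-event row is marked at Day 0, Days 2-10 and initial follow-up, and is blank for long-term follow-up. The list for weeks 8, 12 and 24 in section 8.1.9 has no adverse-event item.

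**Exception.** Under section 10.1.5, serious events after the 30 days are still reported if the investigator judges them at least possibly related.

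**Period of light sensitivity.** Section 6.1.10 states: "Phototoxicity is the most likely potential risk associated with the systemic administration of the porfimer sodium". Section 6.1.7 says "Light-avoidance measures for approximately 30-90 days will be required", and tells patients to "protect the site of the infusion from excessive direct sunlight and certain bright lights for up to 3 months". The background in section 1.1.2 gives a shorter figure: "The photosensitivity usually lasts for 4-6 weeks". Under section 6.1.8 the drug is "given as a single dose 48 ± 4 hours (Day -2) before the EBUS I-PDT".

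**Use of the data.** Section 10.1.3 puts grade 3 and above into the safety analysis; grades 1 and 2 are recorded and reported. Section 12.1.8 tabulates toxicity by grade and sets no time limit of its own. The Cohort B lead-in in section 12.1.9 counts related events of grade 4 or higher.

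**The concern.** The window for recording new reactions closes while patients may still be under light precautions for the risk that the plan ranks as most likely. A sunburn, blister or eye reaction first appearing on day 45 would rarely meet the seriousness criteria of section 10.1.4, so the late-SAE exception would not pick it up. The same holds for a new treatment-related grade 3 event that is not serious, and grade 3 is where the safety analysis begins.

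What is at stake is the completeness of the toxicity tables. Omission can only lower the recorded rate. The overall hypothesis in section 2 includes safety, and section 6.1.10 says that the risk of giving I-PDT two days after palliative radiotherapy is unknown, so the Cohort B tables will be read closely.

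**Working it through.** The plan gives no figure for this point, so there is nothing to reproduce. The check is a day count.

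**Inputs**
- Drug to light: 48 ± 4 h, about 2 days (section 6.1.8).
- Adverse-event window: 30 days after the last intervention (sections 8.1.8 and 10.1.3).
- Length L of the photosensitive period: 28-42 days (4-6 weeks, section 1.1.2) or 30-90 days (light avoidance, section 6.1.7).
- Phototoxicity rates: 3-5% per listed term (section 6.1.10).
- Phase II patients: 18 + 39 = 57 (section 4.1.4).

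**Days covered after the drug**

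Single session: 2 + 30 = 32 days (31.8 to 32.2 with the ± 4 h tolerance).

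**Uncovered time**

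Gap = max(0, L − 32). If onset is uniform over L, the share of first events missed is gap/L. If the hazard falls linearly to zero at L, it is (gap/L)². The documents give no onset curve; both shapes are assumptions.

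| L (days) | Gap (days) | Uniform onset | Linearly falling hazard |
|---|---|---|---|
| 28 | 0 | 0% | 0% |
| 30 | 0 | 0% | 0% |
| 42 | 10 | 10/42 = 24% | (10/42)² = 6% |
| 90 | 58 | 58/90 = 64% | (58/90)² = 42% |

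If a light-only retreatment follows 48 h later (section 8.1.6), coverage is 34 days and the gap is 8 days (19%) for L = 42 or 56 days (62%) for L = 90. The 30 days run from the last intervention, so a later retreatment would lengthen coverage further.

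**Expected counts in 57 patients**
- Per term: 57 × 0.03 = 1.7 to 57 × 0.05 = 2.9 events. The chance of at least one is 82% to 95%.
- Starting after the window, uniform onset, L = 42: 1.71 × 10/42 = 0.4 to 2.85 × 10/42 = 0.7 per term.
- Starting after the window, uniform onset, L = 90: 1.71 × 58/90 = 1.1 to 2.85 × 58/90 = 1.8 per term.

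**Timing of the last query.** The final scheduled adverse-event entry is at 4 ± 1 weeks, so it may fall on day 21. Events between then and day 30 are inside the rule but have no later visit at which they are asked about.

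**The case against.** The strongest reply is that the gap may be small or absent. Light avoidance is a precaution with a margin, not a measured period of risk. The plan's own usual duration is 4-6 weeks: at the lower end nothing is missed, and at six weeks with a falling hazard only about 6% is. This stands, and it is why the result must be given as a range. A reader might infer from 30 covered days out of 90 that two thirds of phototoxicity goes unrecorded. The documents do not support that: it uses only the longest duration, ignores the 4-6 week figure, and overlooks the two days between drug and light.

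A reader might also infer that nothing after day 30 is captured. That is too strong. Related serious events stay reportable under section 10.1.5, and section 10.1.3 allows events already under way to be followed to resolution. Whether late serious events enter the tables is not stated.

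Nor does the gap undermine the safety decision in Cohort B. The lead-in rule counts related events of grade 4 or higher, which would normally be serious and so reportable whenever they occur.

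Two further replies have some force. Safety is a listed objective only for Cohort 0, whose data collection is complete; for Cohorts A and B it appears in the overall hypothesis and as monitoring. And late grade 1-2 reactions would not enter the grade 3 or higher analysis in any case. But section 10.1.3 says the lower grades are to be recorded, section 12.1.8 tabulates by grade, and new non-serious grade 3 events after day 30 are lost as well.

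**Conclusion.** The mismatch is real and limited. New non-serious phototoxicity, and other new non-serious treatment-related events, starting more than 30 days after the last intervention are not systematically collected. The consequence is a downward bias in the descriptive by-grade tables for Cohorts A and B.

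For a single session the uncovered share runs from 0% (28-30 days), through 6-24% (42 days), to 42-64% (90 days). These figures rest on the assumed onset shapes and on which of the plan's durations is taken as the period at risk. In absolute terms, under uniform onset, that is roughly 0.4 to 1.8 events per term among 57 patients for periods of 42 to 90 days. With only 1.7 to 2.9 expected per term, a single missed event visibly changes a row of the table. No formal test or stopping rule depends on it. The correction is worth making because it is cheap.

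**What to change.** 1. Extend collection of new skin and eye phototoxicity of any grade, and of treatment-related events of grade 3 or higher, to the week-8 and week-12 follow-ups.
2. Add the adverse-event entry to the long-term column of Table 1 and to the list in section 8.1.9. That list already has a physical examination and a medication review.
3. Amend the 30-day wording in sections 8.1.8 and 10.1.3 to match, and state in section 12.1.8 which events, by onset date, enter the tables.
4. Reconcile section 8.1.9, which schedules these evaluations, with Table 1 footnote 3, which makes them conditional on clinical need. The query must reach every patient at both time points; otherwise capture would be selective.

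Week 12 falls on day 84 after light, about day 86 after the drug, so nearly all of a 90-day period would be covered at the nominal date. At the early edge of the visit window (week 10) coverage would end at about day 72.

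The cost is a short CRF page at two follow-ups and a slightly higher recorded toxicity rate. Where a visit would not otherwise have taken place, a contact is needed for the query. The change concerns data capture only and leaves doses, precautions and clinical rules as they are.
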